2.1 Study Type

Cluster randomized encouragement design.

2.2 Setting/Location

Research will be conducted through the MyChart electronic medical records system with patients of Inova Health Systems primary care offices (27 locations). Half of the 27 primary care offices will be randomly selected to receive treatment, but outcome data (existing electronic medical records data) will be analyzed for the entire study population.

2.3 Duration of Study

Primary care practices identified in the treatment group will be encouraged to place bulk orders for electronic glucose flowsheets over a period of two weeks. Patients will be actively encouraged to use flowsheets for 12 weeks following the administration period. Outcome data will be collected for a total of 38 weeks:

- (a) 12 weeks retrospective at baseline
- (b) 2 week administration period
- (c) 12 week implementation period
- (d) 12 week follow up period

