3.4 Endpoints/Outcomes Measurements

Hypothesis: Interfacing with primary care practices to encourage physicians to implement default online orders of blood glucose flowsheets and informational messaging for all patients with diabetes will increase patient adoption.

Outcome Measures: Comparison of individuals between treatment and control practices-- (a) fraction of patients entering blood glucose measurements into MyChart flowsheets during implementation period & follow-up period (dichotomous), (b) mean number of flowsheet entries during implementation period and follow-up period (c) fraction of patients for whom order is placed by doctor

Hypothesis: Additional reminder messaging to patients that (1) emphasizes the value of tracking blood glucose data to the patient OR (2) emphasize the value of tracking blood glucose data to the doctor OR (3) informs patient of their selection for a chance to receive an award conditional on tracking will increase adoption relative to no reminder messaging.

Outcome Measure: Comparison of individuals across reminder messaging assignment groups (within treatment practices)-- (a) fraction of patients entering blood glucose measurements into MyChart flowsheets during implementation period & follow-up period (dichotomous), (b) mean number of flowsheet entries during implementation period and follow-up period

Hypothesis: Promotion of adoption of electronic blood glucose tracking through the means described above will result in the following intent-to-treat effects:

(a) reduction in patient A1c

Outcome Measures: Intent to treat comparison of individuals between treatment and control practices of the following measures at the end of the intervention period and follow-up period: (1) Mean A1c (2) Quartiles of A1c using quantile regression analysis (3) fraction of patients experiencing improvement [reduction] in A1c from baseline (dichotomous) (4) fraction of patients below benchmark 7.0% A1c (dichotomous)

(b) increase in frequency of doctor-patient interaction

Outcome Measures: Intent to treat comparison of individuals between treatment and control practices of the following measures during the intervention period and follow-up period: (1) number of securing messaging (2) number of phone interactions, and (3) number of in-office appointments

(c) changes to treatment plan path

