4.1 Sample Size

Non-pregnant adult patients of Inova primary care physicians with a current diabetes mellitus diagnosis and active MyChart account at time of treatment administration will be included in the study. The estimated number of patients is around 7200, from 71 primary care physicians across 24 selected Inova primary care practices.

Power Calculations

Power calculations were performed using the “clustersampsi” command in Stata. Knowledge of available sample and estimates/assumptions of control outcome mean, variance, and intraclass correlation were used to calculate a minimum detectable effect size for the key outcomes of flowsheet adoption (extensive margin, dichotomous rate of adoption) and changes in mean A1c.

Flowsheet Adoption: Practice Level Treatment-Control Comparison

Sample Size: 7200

Number of Treatment Arms: 2

Number of Clusters: 24

Assumed Control Adoption Rate: 2%

Assumed Intra-Cluster Correlation (within practices): 0.1

Minimum Detectable Effect: **9.5 percentage point increase in flowsheet orders**

Mean HbA1c: Practice Level Treatment Control Comparison

Sample Size: 7200

Number of Treatment Arms: 2

Number of Clusters: 24

Assumed Control HbA1c Mean: 6.74

Assumed Control HbA1c Standard Deviation: 1.39

Assumed Intra-Cluster Correlation (within practices): 0.07

Assumed Baseline Correlation: 0.80

ITT Minimum Detectable Effect: **0.27 change in A1c**

Flowsheet Adoption: Individual Level Comparison between Messaging Assignment Groups in Treatment Practices

Sample Size: 3600

Number of Arms (including no reminder): 4

Assumed No Reminder Adoption Rate: 20%

Minimum Detectable Effect: **5.5 percentage point increase in use of flowsheets when compared to no reminder**

Justification

The sample size represents the entire population of Inova primary care patients with diabetes who have active MyChart accounts and are therefore able to access the blood glucose tracking feature. The minimum detectable effects resulting from power calculations above are in-line with similar studies cited in the protocol background. Metastudy reviews of the effect of self monitoring of blood glucose found a 0.33 point change in A1c.

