4.2 Method of Data Analysis

All data analyzed in this study will be administrative health and use data that is collected as part of routine medical care and record keeping. EPIC has offered to build the SQL queries required to produce the outcome datasets described in this protocol. Outcomes listed in Section 3.4. will be analyzed using regression analysis, including (a) a version with no covariates, (b) a version controlling for patient age/gender, race/ethnicity, A1c at baseline, days since most recent office visit at baseline, and doctor fixed effects. A flag identifying patients who are eventual participants of "Impact of Innovative Interventions on Diabetic Adherence with Digital Sensors" (a study recently submitted to the IRB that may have limited overlap with this population) will also be included in the controls. For outcomes indicating analysis of practice level treatment and control groups, standard errors will be clustered at the practice level.

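### The only stated look-back is 12 weeks and baseline A1c is not otherwise defined, so patients last tested earlier have no baseline for the adjusted model or the improvement outcome

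*Combined protocol and SAP*

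**What the plan says.** Section 2.3: "Outcome data will be collected for a total of 38 weeks". The four parts are "12 weeks retrospective at baseline", a 2-week administration period, a 12-week implementation period and a 12-week follow-up period. No other look-back is given.

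A baseline A1c is used in three places:

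- Section 4.2, adjusted model (b), whose covariates include "A1c at baseline, days since most recent office visit at baseline, and doctor fixed effects".
- Section 3.4, the third A1c measure: "fraction of patients experiencing improvement [reduction] in A1c from baseline (dichotomous".
- Section 4.1, where the detectable A1c effect of 0.27 rests on "Assumed Baseline Correlation: 0.80" for a sample of 7200.

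The A1c values are not scheduled by the study. Section 4.2 describes all data as "administrative health and use data that is collected as part of routine medical care and record keeping", and section 2.2 says that "outcome data (existing electronic medical records data) will be analyzed for the entire study population". Eligibility in section 4.1 covers patients "with a current diabetes mellitus diagnosis and active MyChart account at time of treatment administration will be included in the study". It does not require a recent A1c. The plan does not define baseline A1c, set a maximum age for it, or say how patients without one are handled.

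**The concern.** Routine A1c tests are spaced in time, and a short window catches only patients who happened to be tested inside it. A patient with an A1c in the implementation or follow-up window, but whose last earlier test was 13 or more weeks before administration, has a usable outcome and no baseline. Model (b) drops that patient by default, and the improvement outcome cannot be scored.

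The two windows also work against each other. Someone tested in one 12-week window tends not to be tested in the next unless the interval is short. The paired analysis at the end of implementation therefore leans towards frequently tested patients, while section 2.5 expects the study population to resemble the health system's diabetic patients. Because the rule for a missing baseline is open, it could also be chosen after the outcomes are known.

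**Working it through.** **1. The plan's own figure.** Inputs from section 4.1: 7200 patients (3600 per arm), 24 clusters (mean size 300), SD 1.39, ICC 0.07, baseline correlation r = 0.80. Significance level and power are not stated; I assume two-sided 5% and 80%.

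- Design effect: 1 + (300 − 1) × 0.07 = 21.93.
- Standard error: 1.39 × √(2 × 21.93 × (1 − 0.64) / 3600) = 0.0921.
- Multiplier, t on 22 df: 2.932.
- Minimum detectable effect (MDE): 2.932 × 0.0921 = 0.270, which reproduces the stated 0.27.

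**2. Who has a baseline value.** Assume regular testing every T weeks with a random starting phase. The chance of a test in a look-back of W weeks is min(1, W/T).

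| T (weeks) | No value in 12 weeks | No value in 52 weeks |
|---|---|---|
| 13 | 8% | 0% |
| 16 | 25% | 0% |
| 20 | 40% | 0% |
| 24 | 50% | 0% |
| 26 | 54% | 0% |
| 39 | 69% | 0% |
| 52 | 77% | 0% |

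**3. Who has a baseline and an outcome value.** Number the 38 weeks of section 2.3 from zero: baseline 0–12, administration 12–14, implementation 14–26, follow-up 26–38. With T = 26, a baseline value requires a first test in weeks 0–12. The next falls in weeks 26–38, so the implementation window is always missed and the follow-up window always hit. For all intervals:

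| T (weeks) | Implementation, 12-week look-back | Implementation, 52-week | Follow-up, 12-week | Follow-up, 52-week |
|---|---|---|---|---|
| 13 | 85% | 92% | 92% | 92% |
| 20 | 30% | 60% | 30% | 60% |
| 26 | 0% | 46% | 46% | 46% |
| 39 | 0% | 31% | 0% | 31% |
| 52 | 0% | 23% | 0% | 23% |

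The exact zeros come from perfect regularity. If intervals vary by 25% around 26 weeks, the implementation figure with a 12-week look-back is about 10%, against about 46% with 52 weeks. At follow-up it is about 27% against 46%.

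**4. Precision for mean A1c.** Use the formula of step 1.

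- Complete cases, 50% paired (150 per cluster, design effect 11.43): MDE 0.276. At 10% paired (30 per cluster, design effect 3.03): 0.317. The ICC dominates, so losing patients costs little.
- All 7200 kept with a missing-baseline indicator, approximating the variance explained as the covered share × 0.64: 0.324 at 75% coverage, 0.371 at 50%.
- All 7200 with an older, weaker baseline, r = 0.70 for everyone: 0.321.

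**The case against.** The strongest reply is that section 2.3 speaks of outcome data and does not expressly limit covariates. Model (b) uses days since the most recent office visit, which a hard 12-week limit would censor, so a longer look-back for covariates may be intended. This stands as a caveat: applying the 12 weeks to baseline A1c is an inference. But no other window is given, and nothing says which A1c is the baseline.

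Several stronger readings are tempting, and the documents do not support them.

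- *Most patients tested less often than quarterly lack a baseline.* Under regular testing this holds only above a 24-week interval. From 13 to 24 weeks the share is 8% to 50%, and the actual testing frequency is unknown.
- *Only quarterly testers can be paired.* That describes the implementation window. Section 3.4 also measures A1c at follow-up, where patients tested exactly every 26 weeks pair equally well (46%) under either look-back.
- *A longer look-back makes the A1c sample representative.* It does not. The paired shares still fall with testing interval, because the 12-week outcome windows select too.
- *The whole A1c result is compromised.* Model version (a) has no covariates, and the mean, quartile and below-7.0% measures need no baseline value. The look-back precedes the intervention, so treatment should not cause a missing baseline. The issue is coverage.
- *The 0.27 is lost.* Complete-case precision barely moves.

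It can also be said that older values predict less well and may cost more precision than they recover. This stands in part. Taking the most recent value leaves the baseline unchanged for anyone tested in the last 12 weeks, so r = 0.70 for everyone is a worst case.

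**Conclusion.** The point holds in a limited form. Followed as written, the plan drops from model (b) and from the improvement outcome patients who have an outcome A1c but whose last earlier test was more than 12 weeks before administration. The share depends on an assumption the documents cannot settle: under regular testing, 8% lack a baseline at 13-week intervals and 77% at 52. A 52-week look-back raises the paired share at the end of implementation from 30% to 60% at 20-week intervals and from 0% to 46% at 26 weeks. At follow-up it helps at 20, 39 and 52 weeks but not at 13 or 26.

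What is gained is that patients with an outcome are not discarded for want of a recent baseline. Selection through the outcome windows remains. The conclusion rests on two inferences: that the 12 weeks govern the baseline covariate, and that older A1c values can be retrieved, which is plausible given the use of existing records but not stated. The change is worth making before data are extracted; it does not threaten the trial.

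**What to change.** - In section 2.3, extend the retrospective window for A1c only, for example to 52 weeks. If a longer covariate window was always intended, say so.
- In section 4.2, define baseline A1c as the most recent value before the administration period within that window, and add time since that test as a covariate.
- Keep patients with no baseline in the adjusted mean-A1c model with a missing-baseline indicator. For the improvement outcome, state that only patients with a baseline can be scored, and report by arm how many are excluded.
- Confirm before extraction that older A1c values are available.

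The cost is a wider date range in queries that section 4.2 describes as still to be built, a few lines in the protocol, and possibly the data use agreement. No patient contact is needed. On precision, older values may correlate less than 0.80 with the outcome; the worst case above gives an MDE of 0.32, still just under the 0.33 effect cited in section 4.1. The indicator approach costs precision when many baselines are missing (0.371 at 50% coverage), which is a further reason to use the longer look-back alongside it.

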2.4 Number of Subjects

Estimated intake over study duration: 9,000 (only half selected for treatment group). ; Maximum number of subjects: 15,000.

2.5 Study Population

Non-pregnant adult patients of Inova physicians at primary care sites other than Ashburn II Primary Care, Lake Ridge Primary Care and Springfield Primary Care with a current diabetes mellitus diagnosis and active MyChart account at time of treatment administration will be included in the study. There will be no gender, age, racial or ethnic exclusions of adult patients, and study population is expected to match the

distribution of diabetic patient characteristics in Inova health system. Patients will not be formally recruited for participation in the study. The intervention involves practice-level promotion of an existing feature of Inova's MyChart: electronic blood glucose flowsheets. Promotion of this feature will not be formally mandated by the study design. All communications and interactions included in the study will take place electronically through MyChart.

Physicians will exclude from initial bulk flow sheet orders any individual patients whom they identify as having contraindications for tracking of blood glucose.

[figure not shown]

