3.1.1 PRACTICE LEVEL PROMOTION

Providers in the randomly selected group of treatment primary care practices will be encouraged to batch order blood glucose flowsheets for all patients with diabetes with active MyChart accounts. The research team will contact physicians and practice managers with an explanation of the initiative and instructions for completing batch orders and viewing entries through the system. The practice will be advised to complete filling orders over a two week administration period, after which the implementation period will begin. A batch order will trigger two forms of alerts sent to providers, according to the default settings for electronic glucose flowsheets:

1. A bi-weekly report received of values that the patient has entered, or a notification that the patient has not entered data during the interval.
2. A notification when patient entered values are out of range (the patient also gets a notification that their doctor will see this value) according to the following current settings:

Notification Setting	Current Default
Pre-Meal Range (entry outside range=alert)	60-180 mg/dl
Post-Meal Range	100-240 mg/dl
Nighttime Range	60-300 mg/dl

Patients will automatically be notified when the flowsheet has been ordered for them. Additionally, providers will be given text for a secure smart-text message to send to all patients receiving the flowsheets, instructing them to enter data for the study period. The secure message will also provide them with information on how to enter data, and on the benefits of tracking blood glucose. Draft text of this message is included below:

Dear [Patient],

You may have seen that there is a new electronic form available for you to enter your blood glucose results in the MyChart portal. Keeping track of your blood glucose can help you manage your diabetes and reduce your chances for developing complications like heart disease, kidney damage and eye damage. As part of a new Inova program to help patients with diabetes get healthy, I would like you to try entering the results of your home blood glucose tests on MyChart for the next 3 months, through [Date]. Please let me know if you have any questions.

Sincerely,

[Practitioner]

WHAT TO DO NEXT

1. **Get help:** If you need help learning how to measure your blood glucose or getting testing supplies, you can contact [Practice Contact].

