3.3 Randomization

Provider-side treatments will be cluster randomized at the practice level. Randomization will stratify across practices by number of diabetic patients (cluster size), and will be conducted using a random number generator at the outset of the study. Reminder messaging treatments will be assigned alphabetically by first two letters of patient last name, as it is logistically infeasible to do individual level patient messaging without sorting on an existing field in the patient's EHR. There are some concerns that ethnicity could correlate with assignment based on last name spelling, so this form of assignment is "pseudo-random". However, the patient's race/ethnicity recorded in the medical record will be controlled for in the analysis. Causal interpretation of the results of the reminder messaging portion of the experiment will thus require the assumption that grouped last name spelling is not independently related to likelihood of flowsheet adoption.

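### Eligibility is read when treatment is administered, after randomisation and with no common date for control practices; one extract date before practices learn their assignment would close the gap

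*Combined protocol and SAP*

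**What the plan says.** The eligibility rule stands in 2.5, under which adult patients "with a current diabetes mellitus diagnosis and active MyChart account at time of treatment administration will be included in the study", and again in 4.1, where the closing words are the same: "active MyChart account at time of treatment administration will be included in the study". Both sections also require that the patient is not pregnant.

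On assignment, 3.3 says "Provider-side treatments will be cluster randomized at the practice level", and that this "will be conducted using a random number generator at the outset of the study". Randomisation is stratified by each practice's number of diabetic patients.

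Section 2.3 places a two-week administration period between the 12-week retrospective baseline and the 12-week implementation period. In that period the research team contacts physicians and managers of treatment practices (3.1.1), whose providers are "encouraged to batch order blood glucose flowsheets for all patients with diabetes with active MyChart accounts". Control practices get no encouragement (3.2).

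Section 2.4 gives the number of subjects as "Estimated intake over study duration: 9,000"; 4.1 uses about 7,200 for power.

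No section gives a calendar date for eligibility, says that the patient list is drawn before practices learn their assignment, or names an index date for control practices.

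**The concern.** Nobody is individually recruited (2.5, 2.6), so the intent-to-treat contrast depends on identifying patients in the same way in both arms. The cohort is the denominator for the order fraction, the fraction entering data and the mean number of entries, and it fixes the case mix for A1c, visits and messages (3.4).

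A rule read at administration is read after assignment, and possibly after treatment practices have been contacted. The fields that define eligibility (recorded diagnosis, account status, pregnancy status) are ones that a practice can update. If contact led some treatment practices to activate accounts or record diagnoses, those patients would enter the cohort in one arm only, and they would probably be more engaged than average. Adjustment would not reliably remove this: version (a) of the regression in 4.2 has no covariates, and version (b) has no measure of motivation to track.

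**Working it through.** **Order of events.** Randomisation comes at the outset (3.3). Contact and ordering in treatment practices follow, over two weeks (2.3, 3.1.1), and eligibility is read at administration (2.5, 4.1). The text allows a reading on the first day, before any contact, and equally one on any later day of the window. For control practices the window exists on the study timeline, but no day within it is named.

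**The plan's own figures.** Inputs from 4.1: 7,200 patients and 24 practices, hence 3,600 patients and 12 practices per arm and 300 per practice on average. Two-sided alpha of 0.05 and 80% power are assumed, as the documents state neither. With 22 degrees of freedom the multiplier is 2.074 + 0.858 = 2.932.

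- A1c: design effect 1 + 299 × 0.07 = 21.93. SE = 1.39 × √(2 × 21.93/3,600) × √(1 − 0.80²) = 0.092. Minimum detectable effect = 2.932 × 0.092 = 0.27, as stated.
- Adoption: design effect 1 + 299 × 0.1 = 30.9, effective n = 3,600/30.9 = 116.5 per arm. From a 2% control rate the detectable rise is 9.4 points (unpooled variance) or 9.6 points (pooled), against the stated 9.5. The implied SE is 9.5/2.932 = 3.2 points.

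**Shift in adoption.** Let b be adoption among patients who would be in the treatment-arm cohort anyway, e the extra patients as a share of them, and q adoption among the extra patients. The shift is (b + e·q)/(1 + e) − b = e(q − b)/(1 + e). The documents give no e, so 1 to 5% is an assumption. For q, 4.1 offers 20% (its assumed no-reminder rate in treatment practices) and 25.5% (that rate plus its detectable rise of 5.5 points).

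| b | e | q | Shift (points) |
|---|---|---|---|
| 10% (assumed) | 1% | 20% | 0.01 × 0.10/1.01 = 0.10 |
| 10% (assumed) | 5% | 25.5% | 0.05 × 0.155/1.05 = 0.74 |
| 20% (rate in 4.1) | 5% | 25.5% | 0.05 × 0.055/1.05 = 0.26 |
| 2% (control rate) | 5% | 60% (assumed) | 0.05 × 0.58/1.05 = 2.76 |

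The first two rows give the range of about 0.1 to 0.7 points. The upper end is 0.74/3.2 = 0.23 of a standard error. If the extra patients adopt at the same rate as the rest, the shift is zero. The last row is extreme: the promotion does nothing for existing patients, while 60% of newly added ones enter data.

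**Shift in mean A1c.** If a fraction f of the treatment-arm cohort is there only because of the promotion and differs by d from the rest, the bias is f × d. Both are assumptions.

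| f | d | Bias | Share of 0.27 | Type I error |
|---|---|---|---|---|
| 1% | 0.5 | 0.005 | 2% | 5.0% |
| 5% | 0.5 | 0.025 | 9% | 5.8% |
| 5% | 1.0 | 0.050 | 19% | 8.2% |

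The type I errors pair an unadjusted bias with the baseline-adjusted SE of 0.092, so they lean towards the pessimistic side.

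**With a fixed list.** Both e and f are zero, so this source of bias is zero. The stated detectable effects do not change if about 7,200 patients remain.

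**The case against.** The strongest reply is that the mechanism is conjecture, and much of that reply stands.

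- Nothing in the documents asks staff to activate accounts or add diagnoses. Section 3.1.1 directs orders at patients who already meet both criteria, and 2.5 keeps all study communication within MyChart, so patients without an account could be drawn in only indirectly, within two weeks.
- The window in 2.3 can be applied to control practices as well. What is missing is the day, not any possible date.
- A snapshot may have been intended. Section 4.1 describes the sample as the whole population with diabetes and an active account, outcome data are routine records obtained by query (4.2), and stratification in 3.3 needs practice counts before randomisation. However, 3.3 counts diabetic patients per practice and does not tie the cohort to a list.
- Some protection is already there: 2.5 lets physicians leave patients out of the bulk order, not out of the cohort, and 3.5 foresees examining outcomes regardless of flowsheet use.

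A reader might also infer from the intake wording in 2.4 that patients enter on a rolling basis, or that the gap of 9,000 − 7,200 = 1,800 consists of later entrants. The documents do not support this. Section 2.5 sets a criterion at a point in time, and nothing says what the gap represents. The wording is loose and should be aligned.

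What the reply does not remove is the rule itself: as written, membership is settled after assignment, and no safeguard is stated.

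**Conclusion.** The point holds as a gap in the definition of the cohort. Eligibility is tied to an activity that follows randomisation, lasts two weeks and takes place in one arm, with no common index date. This leaves a one-sided route into the cohort that is possible but unproven.

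A reader might infer that the intent-to-treat comparisons are biased, or that the promotion will enlarge the treatment cohort. The documents show neither. Under 1 to 5% induced entry (assumed), adoption of 20 to 25.5% among those patients (from 4.1) and a 10% base (assumed), the shift is about 0.1 to 0.7 points against a detectable effect of 9.5. It reaches 2.8 points only under extreme assumptions. The effect on mean A1c is likely to be small. If the list is in fact drawn before any practice is contacted, this bias disappears, but the protocol does not say so. This is a cheap improvement: worth making because it costs almost nothing, not because a bias of consequence has been shown.

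**What to change.** In 2.5 and 4.1, replace the reference to treatment administration with one electronic-record extract, taken on the same calendar date for all practices and before any practice is told its assignment. Read diagnosis, account status, adult age and pregnancy status on that date, and fix each patient's practice and doctor on it. Analyse every listed patient in the assigned practice, including those whom a physician leaves out of the bulk order. Patients who become eligible later may use the flowsheet but are not in the analysis cohort. Align the intake wording in 2.4 with this definition. As an optional check, report new account activations and new diagnoses by arm after the extract date.

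The cost is one query date and a change of wording, since record queries are planned anyway (4.2). Physicians' decisions about individual patients are untouched. The downside is that patients who become eligible in the weeks after the extract are not analysed.
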